#### **8.4 STATISTICAL ANALYSIS**

Adverse events, SAEs, and events of interests will be summarized by treatment group, and by the three categories of treatment status and treatment group using percentage and frequency. For abnormal laboratory results assessed as AEs (clinically significant abnormal laboratory results), reported values of laboratory results in the course of AE follow-up will be summarized descriptively, including mean, standard deviation (SD), median, minimum and maximum. Categorical or qualitative variables will be summarized using percentages and frequency distributions. Timing of CYP2D6 genotyping and prevalence of CYP2D6 predicted phenotypes and GD subtype among Cerdelga-treated patients will be summarized using percentages and frequency.

In addition, the 95% confidence interval of incidence rates will be provided by treatment group. The risk of any AE in the Cerdelga group compared to Cerezyme will be evaluated in terms of the risk ratio with associated 95% confidence interval.

Data will be analyzed as available, missing data will not be imputed. For all AEs summary statistics, frequencies, cumulative incidence, and incidence rates per person-time will be calculated as appropriate. All summaries will be descriptive; no formal hypothesis testing will be performed.

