**Protocol amendment summary of changes table**

Section # and Name	Description of Change	Brief Rationale
Section 4, Abstract, Variables, Analysis of endpoint; Section 8.2.3, Analysis population(s); Section 8.8, Data Analysis	Revised text (replacement of “adjusted for” by “considering”) to specify that the main analysis of interest will be the incidence rate of any AE report for Cerdelga treated patients during participation in the sub-registry, considering treatment status at sub-registry enrollment (if applicable).	Clarification (“adjustment” was a statistical term dedicated to comparisons).
Section 4, Abstract, Analysis of endpoint	Revised text to specify that the primary endpoint will be the incidence rate of any AE report for Cerdelga treated patients during participation in the sub-registry, considering treatment status at sub-registry enrollment (if applicable).	To align with Section 8.8, Data analysis.
Section 4, Abstract, Data analysis, Analysis of endpoint; Section 8.8.2, Secondary Analysis	Removal of secondary analysis/endpoint: change from the initial clinically significant abnormal laboratory results.	As noted by the PRAC, the analysis is part of the ICGG Gaucher Registry.
Section 4, Abstract, Data analysis; Section 5, Milestones; Section 8.8.4, Interim Analysis	Revised text to specify that interim analysis is planned two years after the last Cerdelga patient has been enrolled in the study.	To reflect amendment specific changes - to align with the revised proposal for end of data collection.
Section 4, Abstract, Milestones; Section 5, Milestones; Section 8.2, Setting; Section 8.2.1, Duration of the study	Revised proposal for end of data collection: Data collection will be concluded four years after the last Cerdelga patient has been enrolled into the study.	Extension of enrollment period by approximately one year to enroll more Cerdelga patients than originally planned and duration of safety follow up ranging from 4 years to up to 6.5 years will provide long-term safety data on Cerdelga for a sufficient number of patients.

Section # and Name	Description of Change	Brief Rationale

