#### Important potential risks:

- Drug-drug interactions:
  - Use with CYP2D6 and/or CYP3A inhibitors
  - Use with strong CYP3A inducers
  - Use with P-gp or CYP2D6 substrates

- Use of Cerdelga in patients who are CYP2D6 indeterminate metabolizers or non-genotyped patients
- Cardiac conduction disorders and arrhythmias

Missing information:

- Use in patients with a history of or current cardiac ischemia or heart failure, clinically significant arrhythmias or conduction findings
- Use during pregnancy and lactation
- Safety in long-term treatment use
- Use in patients who are CYP2D6 URM

Available published and unpublished data related to gaps in knowledge reflect the current information presented above and in the EU RMP.

Additional pharmacovigilance activities beyond routine to gather long-term safety data are needed to explore and further characterize this missing information. As European Authorities have identified the limited number of exposed patients, particularly in real-world experience and in the long-term, as a major concerned area of research given that Cerdelga is intended to be a chronic treatment, long-term data will provide a better understanding of the potential risks that were identified in clinical studies and may clarify whether these risks are due to Cerdelga treatment, the underlying GD, or another cause.

Finally, the sub-registry will allow assessment of clinical practice and prescribing patterns, and the adherence of prescribing HCPs to Cerdelga key label (prescribing information) requirements, and will provide data to assess the effectiveness of risk minimization measures. Key prescribing information requirements include testing the genotype and predicting the phenotype of the key metabolic pathway, CYP2D6, in each patient before starting treatment to guide dosing; excluding CYP2D6 indeterminate and URM from treatment; and prescribing Cerdelga only to patients with type 1 GD.

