## 7 RESEARCH QUESTION AND OBJECTIVES

### 7.1 PRIMARY OBJECTIVE

The primary objectives:

1. To evaluate the long-term safety of Cerdelga in real-world clinical practice.
2. To describe the utilization of Cerdelga.

The long-term safety of Cerdelga will be evaluated by the incidence rate of any AE during sub-registry participation, whether considered related or unrelated to Cerdelga by the treating HCP. The risk of an AE compared to Cerezyme will be evaluated in terms of the risk ratio (ratio of incidence rates).

Evaluation of utilization patterns of Cerdelga includes:

- To assess compliance/adherence of HCPs to the labelling with regard to CYP2D6 genotyping prior to initiation of Cerdelga
- To assess compliance/adherence of HCPs to the Cerdelga label with regard to patients' CYP2D6 predicted phenotype
- To assess compliance/adherence of HCPs to the Cerdelga label with regard to use in GD type 1.

In order to avoid the introduction of an element of positive or negative bias into the safety reporting from the ICGG Gaucher Registry physicians by providing a specific list of safety issues to be collected (and subsequently recorded in the CRFs) in protocol, there will be no suggested areas of safety data collection. Rather all safety data will be collected and subsequently assessed in relation to the important potential risks in the RMP. All AEs for Cerdelga and Cerezyme, regardless of their relation to treatment will be collected. However, when the safety analysis will be performed, specific exploratory analyses of the potential risks listed in RMP and any new safety concern that could arise from the sub-registry, will be included and reported in the PSUR in the EU regional annex.

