### **8.2.2 Eligibility criteria**

#### **8.2.2.1 Inclusion criteria**

Patients must meet the following criteria to be eligible to participate in the safety sub-registry:

- I 01. Male or female patient aged 18 years or older;
- I 02. The patient must be enrolled in the ICGG Gaucher Registry prior to safety sub-registry enrollment;
- I 03. The patient is willing and able to provide written informed consent for the safety sub-registry;
- I 04. The patient must have a confirmed diagnosis of GD, as defined in the protocol of the ICGG Gaucher Registry (documented acid  $\beta$ -glucosidase deficiency and/or mutations in the acid  $\beta$ -glucosidase gene);
- I 05. The patient must either initiate or continue treatment with Cerdelga or Cerezyme at the time of safety sub-registry enrollment.

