### **8.3 VARIABLES**

The main analysis of interest will be the incidence rate of any AE report for Cerdelga-treated patients during participation in the sub-registry.

The outcome variable will be a report of an AE, exposure will be duration (in months or years) of time of exposure to Cerdelga while enrolled in the sub-registry, grouping factors will include category of Treatment Status (defined below), duration of GD treatment (including Cerdelga or other GD treatments) prior to enrolling in the sub-registry, selected demographic and baseline characteristics such as age, sex, and genotype as listed in [Section 8.7.5](#).

Category of treatment status at the time of sub-registry enrollment will be defined as:

- a) Patients naive to any GD treatment (ERT or SRT). This category will include, for example, newly diagnosed patients.
- b) Patients naive to the product of interest (Cerdelga in the Cerdelga group and Cerezyme in the comparator group) but experienced to any other treatment for GD (ERT or SRT). This category will include, for example, patients who will switch from any one therapy to the product of interest.
- c) Patients experienced to the treatment of interest. This category will include patients who were on treatment with the product of interest at entry into the sub-registry and then continue this therapy.

Note:

- Patients whose first GD treatment is commercial Cerdelga or Cerezyme, and who enroll in the sub-registry within 3 months of the first dose will be considered treatment naive for the purposes of analysis. Regardless of prior treatment, these patients must receive either Cerdelga or Cerezyme during their participation in the sub-registry.
- Previous exposure to Cerdelga in clinical studies will be considered for any patient of the sub-registry, notwithstanding the group of treatment they belong to during sub-registry participation.
- The data for enrolled patients who switch treatment from the Cerdelga to the Cerezyme or vice-versa during follow-up will be evaluated to and from the point of switch in the therapy.

- A subset of treatment experienced patients will be patients who will switch from any one therapy to any other therapy.
- When available, AEs reported by the patient and in the opinion of investigator related to Cerdelga intake and Cerezyme administration (prior to enrollment into the safety sub-registry) will be collected as part of the patient enrollment characteristics (medical history).

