### **8.10 LIMITATIONS OF THE RESEARCH METHODS**

During the clinical studies the frequency of AEs had a tendency to decrease over time. To control for a possible relation between the frequency of AEs and the duration of treatment, AEs will also be analyzed after stratification of patients between three categories of treatment status.

For the sub-registry to meet its goal of providing real-world information on Cerdelga safety, the design of the study must ensure that HCPs report all AEs without preconceived ideas on the safety profile of Cerdelga. To this end no AESI have been specified.

To determine if there are any differences between patients who accept to enroll in the sub-registry and those who do not and, if these differences have any impact on the generalizability of the results, baseline characteristics (including age, sex, genotype, GD history, GD treatment history, current GD treatment and CYPD phenotype) of patients who were enrolled in the safety sub-registry will be compared based on provisions of ICGG Gaucher registry ICF with baseline characteristics of ICGG Gaucher registry patients who did not accept to enroll into safety sub-registry, if this information can be obtained.

Baseline characteristics of subjects who discontinue the study and subjects who complete the study will be summarized in the clinical study report. In addition, number and percent of subjects who discontinue the study will be provided.

The patients enrolled in the ICGG safety sub-registry are not expected to have an extra burden of physician visits or out of the standard of care procedures/tests to comply with, thus any drop out would be mostly expected for reasons not related to the safety sub-registry or for patients who transfer from either Cerdelga and Cerezyme to another GD treatment.

The number of patients for both of the groups who continue their observation in the safety sub-registry will be evaluated annually after the end of the recruitment period to determine the need to replace patients who dropped out of the study for any reason. The need to continue with this requirement will be reassessed two years after the last Cerdelga patient has been enrolled in the study in the interim report.

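### The only Cerdelga-versus-Cerezyme effect measure is an unadjusted rate ratio between HCP-chosen groups; the planned stratification by treatment status never reaches it

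*Combined protocol and SAP*

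**What the plan says.** - **The comparison.** Section 8.4: "The risk of any AE in the Cerdelga group compared to Cerezyme will be evaluated in terms of the risk ratio", with a 95% confidence interval. Section 7.1, under the primary safety objective, defines this as a ratio of incidence rates. No covariates, strata or weights are named in either place, and no other between-group effect measure is specified.
- **Allocation.** Section 8.1 leaves all treatment decisions to the HCP. Section 8.2 plans roughly two Cerdelga patients per Cerezyme patient.
- **Time and treatment status.** Section 8.10: "During the clinical studies the frequency of AEs had a tendency to decrease over time". Its next sentence responds by planning to analyse AEs stratified by the three treatment-status categories. Section 8.4 summarises AEs by status and treatment group as frequencies and percentages. Section 8.8 estimates status-specific incidence rates in both groups if there are enough data.
- **Other factors.** Section 8.3 lists as grouping factors treatment status, "duration of GD treatment (including Cerdelga or other GD treatments) prior to enrolling in the sub-registry", and age, sex and genotype. No method connects them to the ratio.
- **GD type.** The inclusion criterion in Section 8.2.2.1 reads "The patient must have a confirmed diagnosis of GD, as defined in the protocol of the ICGG Gaucher Registry" and sets no limit on type. Section 6.2 counts "prescribing Cerdelga only to patients with type 1 GD" among the key label requirements. GD type is collected at enrolment (Section 8.7.5), but Sections 8.4 and 8.8.1 plan its frequencies for Cerdelga-treated patients only.
- **Expected value.** Section 8.6.1 expects a ratio of about 1.2, based on treatment-experienced patients in the registration study.

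**The concern.** Section 6.1 gives comparison with Cerezyme as a purpose of the sub-registry and hopes the data may show whether certain AEs come from the drug, the disease or another cause. A ratio with a confidence interval will be read as an answer to that. If AE frequency falls with time on treatment, a different mix of naive, switched and long-treated patients moves the ratio without any drug effect. If some non-GD1 patients enrol, the label makes it likely that most of them are on Cerezyme, and a different AE rate in them would also move the ratio.

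The plan recognises the underlying problem in two places. Section 8.10 wants to control for duration of treatment. Section 6.2 rejects miglustat as comparator because its users would come from a different underlying population. Yet Section 8.10 does not mention confounding between Cerdelga and Cerezyme. Its baseline comparisons are of enrolled with non-enrolled patients and of discontinuers with completers, not of one treatment group with the other.

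**Working it through.** **The plan's own figures.** The detection statement in Section 8.6.1 reproduces: 1 − 0.95^100 = 0.994, which is more than 95%. It does not bear on the comparison. The expected 1.2 cannot be reproduced, because no group rates are given.

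**Formula.** Let pT and pC be the shares of person-time at a raised AE rate in the Cerdelga and Cerezyme groups, and k the factor by which that rate is raised. Then

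crude ratio = true ratio × [1 + pT(k − 1)] / [1 + pC(k − 1)].

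The shares must be of person-time, because Section 7.1 defines a ratio of incidence rates. The documents give none of pT, pC or k. Every value below is an assumption.

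**Recent starters, no drug effect.** Assume they are 30-40% of Cerdelga and 5-10% of Cerezyme patients, k is 1.5 to 2, and every patient has four years of follow-up. If the excess lasts one year of four, each share is multiplied by 1/4; if two years, by 1/2.

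| Excess lasts | Low end (30% vs 10%, k = 1.5) | High end (40% vs 5%, k = 2) |
|---|---|---|
| All follow-up | 1.15/1.05 = 1.10 | 1.40/1.05 = 1.33 |
| Two years of four | 1.075/1.025 = 1.05 | 1.20/1.025 = 1.17 |
| One year of four | 1.0375/1.0125 = 1.02 | 1.10/1.0125 = 1.09 |

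**Imbalance needed to produce 1.2 alone.** Solving for pT with pC = 10% gives pT = [1.2(1 + 0.1(k − 1)) − 1]/(k − 1). That is 52% at k = 1.5, 32% at k = 2 and 22% at k = 3, as shares of person-time.

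**GD type.** Suppose non-GD1 patients are found only on Cerezyme, with share g. A true 1.2 then reads 1.2/[1 + g(k − 1)]. With g = 5% and k = 2 this is 1.2/1.05 = 1.14. With g = 10% and k = 3 it is 1.2/1.20 = 1.00.

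**What a stratified ratio does.** Assume 400 and 200 person-years (100 and 50 patients for four years, no dropout), 0.5 AEs per person-year in the low-rate stratum, k = 2 throughout, and Poisson counts.

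- True ratio 1.0, shares 40% (Cerdelga) and 10% (Cerezyme). Expected events are 160 + 120 = 280 and 20 + 90 = 110. The crude ratio is (280/400)/(110/200) = 1.27 (95% CI 1.02-1.59). Mantel-Haenszel gives 1.00 (0.79-1.27).
- True ratio 1.2, shares reversed. The crude ratio is 0.94 (0.77-1.16). Mantel-Haenszel gives 1.20 (0.96-1.50).

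In the first case the ratio of upper to lower limit rises from 1.55 (crude) to 1.60 (stratified), so the loss of precision is small. Repeated AEs within a patient would widen all these intervals.

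**The case against.** **The plan is not blind to treatment status.** Stratified AE summaries, and conditional status-specific rates in both groups, let a reader compare within strata. This stands, and it would be wrong to infer that the plan makes only a crude comparison. But the summaries are frequencies and conditional rates. They give no within-stratum or pooled ratio, and nothing changes the one that carries a confidence interval. Annex 4, in the history of amendment 03 (which was not implemented), says preliminary data suggested the status subgroups might be too small to analyse. That favours a pooled stratified estimate over separate tables.

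**Differences between the groups are possible, not shown.** This also stands. No distribution of status, prior treatment or GD type is given. Sites are those managing GD1, and recruitment aims to represent GD1 patients, which limits any GD-type imbalance without excluding it.

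**The comparison is descriptive.** The primary endpoint is the Cerdelga incidence rate, the ratio is absent from the lists in Sections 8.8.1 to 8.8.3, and no test is planned. That lowers the stakes. It does not remove bias from a reported ratio. Sampling error is also large: a true, unconfounded 1.2 has a 95% CI of 0.95-1.52 under the person-time assumptions above with a Cerezyme rate of 0.5 per person-year. Adjustment will not make 1.0 and 1.2 clearly distinguishable at that rate.

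**The amendment wording.** Amendment 04 dropped the language of adjustment because adjustment "was a statistical term dedicated to comparisons". A reader might infer that the sponsor removed an adjustment from the ratio. The change concerned the single-group Cerdelga rate. What can fairly be said is that the stated reason points to the comparison, and the comparison has no adjustment.

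**Conclusion.** The concern holds in a limited form. The one between-group effect measure is unadjusted, the groups are not randomised, and the stratification that the plan itself considers necessary is not carried into it. The crude ratio can therefore be confounded in either direction, by an amount the documents do not allow anyone to fix.

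A reader might go further and conclude that the groups do differ, or that time on treatment alone will create or hide the expected 1.2. The documents do not support that. Under the assumed shares and rates, a ratio of 1.10 to 1.33 with no drug effect requires the excess to last throughout follow-up, which fits poorly with an AE frequency that falls over time. An excess confined to one year of four gives about 1.02 to 1.09. The GD-type figures rest equally on assumption.

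The point does not touch the primary endpoint. It matters because the ratio sits under the primary safety objective, and because covariates chosen after the data are seen would carry less weight.

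**What to change.** 1. In Sections 8.4 and 8.8, pre-specify one Cerdelga/Cerezyme rate ratio to be reported beside the crude one. Use either a Mantel-Haenszel ratio on person-time stratified by treatment status, or a robust Poisson model with log on-treatment time as offset, adjusting for treatment status, age and sex. Choose between them now.
2. Add a sensitivity analysis restricted to GD1 patients in both groups.
3. Tabulate GD type, treatment status, prior treatment and demographics for Cerezyme as well as Cerdelga.
4. Name confounding between the treatment groups as a limitation in Section 8.10.

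The cost is wording and programming, since the variables are already collected. The downsides are a somewhat wider interval and, for the model, some dependence on its form with about 150 patients. Neither method rescues sparse or non-overlapping status strata. These contribute little information and should be reported as such.

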#### **8.5 DATA SOURCES**

The data source for the ICGG sub-registry study is all patients enrolled in the ICGG Gaucher registry who are Cerdelga or Cerezyme treatment naive or continue treatment with Cerdelga or Cerezyme. The ICGG Gaucher Registry is a multi-center, international, longitudinal, observational program for patients with GD designed to track the natural history and outcomes of patients. The ICGG Gaucher Registry database has been designed to collect a variety of baseline and follow-up data obtained through routine clinical and laboratory assessments.

Data in the ICGG sub-registry study will be collected from enrolled patients by participating HCPs at the time of all patient office visits occurring as per local practice visit schedule or following the recommended schedule of assessments of the ICGG Gaucher Registry. Information that is shared by the Registry and sub-registry will be collected only once. Information specific to

the sub-registry will be collected in specifically designed CRFs. Data collected by sub-registry HCPs or their designees will be submitted to the sub-registry for central processing and evaluation. A primary contact person located at the participating site should be designated as the individual responsible for completing and entering CRFs into the sub-registry database.

## **8.6 STUDY SIZE**

### **8.6.1 Determination of sample size**

The sample size determination was not based on power consideration. The sample size of at least 100 patients on Cerdelga was chosen to provide a sufficient number of patients to describe the real-world safety profile of Cerdelga. With 100 patients on Cerdelga, there is more than 95% of probability of observing at least one patient with an AE if the true cumulative rate of such an event is 5%. In addition, it is a similar size (n=106) to the number of Cerdelga patients treated in the primary analysis period of the ENCORE registration study (1) which was a direct comparison of Cerdelga to Cerezyme and should then confirm the safety profile experienced in a real-world setting. Accordingly, a control group of safety sub-registry to descriptively compare the safety profile of Cerdelga to that of Cerezyme will include approximately 50 patients on Cerezyme.

Based on the treatment experienced patients in the ENCORE study, the risk ratio of any AE comparing Cerdelga to Cerezyme is expected to be approximately 1.2.

